Support: Department of Neurobiology and Dev. Scs.

Exclusion Criteria

- 1) a personal or family history of epilepsy,
- 2) severe head injury, aneurysm, stroke, previous cranial neurosurgery,
- 3) severe or recurrent migraine headaches,
- 4) metal implants in the head or neck, a pacemaker,
- 5) pregnancy,
- 6) medications that lower seizure threshold,

Aim 3

Up to ten subjects from a previous study (109033) will be invited to participate. Subjects enrolled in this study were between the ages of 21 and 85. Subjects will have already passed the following eligibility criteria for 109033 but they must indicate that they still meet the following eligibility criteria to be eligible for this study.

Inclusion Criteria

- 1) Report experiencing the presence of their phantom auditory perception for at least 6 months
- 2) Complete and pass the Transcranial Magnetic Stimulation Adult Safety Screen (TASS).
- 3) Female subjects of childbearing age must take a pregnancy test to rule out pregnancy prior to participating in this study.
- 4) Individuals taking SSRIs and benzodiazepines or for depression or anxiety related to tinnitus must be stable on doses of these medications for 3 months and not change medications during the course of the study.
- 5) Patients who agree to have an MRI scan must pass screening procedures for an MRI scan.

Exclusion Criteria

- 1) A clinical, personal or history of epilepsy, including a first degree relative diagnosed with epilepsy.
- 2) Head injury that resulted in the loss of consciousness for more than 10 minutes.
- 3) Aneurysm, stroke, previous cranial neurosurgery, diagnosed neurological or major psychiatric disorders (excluding depression or anxiety related to tinnitus).
- 4) Ferromagnetic metal implants in the head or neck, pacemaker.

Study Title: Regulating homeostatic plasticity and the physiological response to rTMS
PI: [name]
Institution: University of Arkansas for Medical Sciences
Support: Department of Neurobiology and Dev. Scs.

- 5) Medications that lower seizure threshold or reduce cortical excitation. These medications include some antidepressants (i.e., tricyclic antidepressants and bupropion) and anticonvulsants.
- 6) Significant neurological disease, acoustic neuromas or glomus tumors, active Meniere's disease, or profound hearing loss (>90 dB at 4000 Hz).
- 7) Bipolar Disorder.

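### Aim 3 bars only ferromagnetic head or neck implants, while Aims 1 & 2 bar any metal implant there for the same kind of stimulation, and no safety reason is given

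*Combined protocol and SAP*

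**What the plan says.** Study Population has two eligibility lists.

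- **Aims 1 & 2** (20 healthy volunteers): exclusion item 4 is "metal implants in the head or neck, a pacemaker", and item 3 is "severe or recurrent migraine headaches".
- **Aim 3** (up to ten tinnitus patients from study 109033): exclusion item 4 is "Ferromagnetic metal implants in the head or neck, pacemaker". Migraine is not named. The nearest entries are item 3, which includes diagnosed neurological disorders, and item 6, which begins "Significant neurological disease, acoustic neuromas or glomus tumors".

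The Aim 3 list is carried over from 109033. Former participants have passed it once, and "they must indicate that they still meet the following eligibility criteria to be eligible for this study". Both parts also use the TASS.

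Under Apparatus, Materials, and Procedures, Aim 3 is said to use the Aims 1 & 2 methods for tDCS and rTMS. The stated exceptions are a different cap, 1800 rather than 900 pulses, and active 1 Hz delivery only.

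**The concern.** Where two parts of one protocol share devices, stimulation site and intensity, one would expect the same device-safety exclusions, or a stated reason for any difference. Here a subject with a non-ferromagnetic metal implant in the head or neck is excluded by one list, while the implant item of the other list does not reach that subject. The only explanation offered is that the Aim 3 list came from 109033. That is where the list came from, not a safety argument, and tDCS is an addition relative to the earlier work.

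The protocol relies heavily on these lists. Protection Against Risks Associated with TMS presents careful screening as the main safeguard and expects the exclusion criteria to remove people at higher risk. A narrower item in the part with more active stimulation therefore needs either a reason or a correction. What is at stake is consistent screening; no endpoint, estimate or test depends on it.

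**Working it through.** The plan states no figure on this point, so the check compares the two parts side by side.

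**1. Exposure per subject** (Table 1; Aim 3 under Study Design; Apparatus, Materials, and Procedures). Only treatment pulses are counted, not the single pulses used for EEG probing.

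| | Aims 1 & 2 | Aim 3 |
|---|---|---|
| rTMS site, intensity | TC, 110% of motor threshold | TC, 110% of motor threshold |
| rTMS rate | 1 Hz or 10 Hz | 1 Hz |
| Pulses per session | 900 (10 Hz: 45 trains × 2 s × 10 per s = 900) | 1800 |
| Active rTMS sessions | 2 (conditions 2 and 3) | 3 (visits 2 to 4) |
| Active rTMS pulses | 2 × 900 = 1800 | 3 × 1800 = 5400 |
| Spacing | at least two weeks | within one week |
| tDCS dose | 2 mA, 20 min | 2 mA, 20 min |
| tDCS site | TC (Aim 1) or DLFC (Aim 2) | DLFC |
| Active tDCS | 1 × 20 = 20 min (condition 3) | 3 × 20 = 60 min |

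Aim 3 gives 1800/900 = 2 times the pulses per session, 5400/1800 = 3 times the active pulses in total, and 60/20 = 3 times the active tDCS. One sentence in the Protocol Summary speaks of four treatment days. The visit schedule and the procedures section both give three, which is used here; four would only widen the gap. A lower exposure therefore cannot explain the narrower implant rule, apart from the pulse rate, which is taken up in the objection.

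**2. Implant item.** Both lists name metal implants in the same body region and a pacemaker. The difference is the word *ferromagnetic* in Aim 3. This is a written rule with a narrower scope, not an omission.

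**3. Do other steps in Aim 3 close the implant gap?**
- *MRI metal form.* It is completed before the scan. The Aim 3 visit description makes the scan optional, and inclusion item 5 applies only to those who agree to it, so the form does not reach every subject. The other MRI metal check is a ferromagnetic detector, which targets the same narrower class as item 4.
- *Re-confirmation at entry.* It uses the same 109033 list and so repeats the narrower implant item.
- *TASS.* It may ask about implants; its items are not in the documents. Aims 1 & 2 also use the TASS and still list all metal implants separately, so in that part the sponsor did not treat the questionnaire as a replacement for the item.

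**4. Migraine.** Aims 1 & 2 name it and Aim 3 does not. Items 3 and 6 may cover a diagnosed migraine, depending on how the screener reads them, and the TASS may cover it too. The documents establish that migraine is not named in Aim 3. They do not establish that it is allowed.

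**The case against.** The strongest defence has five parts.

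- **Unseen screen.** Every Aim 3 subject must pass the TASS. Without its items, nobody can say from the documents that an implant or migraine would get through. This stands. It limits the point to the wording of the list.
- **Different risk profile.** Aims 1 & 2 include a 10 Hz arm, and Risks Associated with TMS ties reported seizures almost entirely to high-frequency rTMS. That could partly justify a stricter list for Aims 1 & 2. However, the 1 Hz subjects in Aims 1 & 2 face the same strict list, and the protocol does not offer this reason.
- **Prior exposure.** Aim 3 subjects have already completed active 1 Hz rTMS, and the safety section rates tDCS as the lower-risk device. This lowers the practical risk. It does not cover an implant acquired since 109033.
- **No stated hazard.** The TMS and tDCS risk sections describe no danger from non-ferromagnetic metal and no added risk in migraine; metal in the body is discussed there only for MRI. This stands. The point rests on the inconsistency between the sponsor's own two rules, not on a documented hazard.
- **Selective comparison.** A reader might infer that the Aim 3 list is looser overall. It is not: it is stricter on diagnosed neurological and psychiatric disorders, bipolar disorder, abnormal head imaging and drugs that reduce cortical excitation.

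A reader might also treat the head-injury wording as part of the same fault, since Aims 1 & 2 say "severe head injury, aneurysm, stroke, previous cranial neurosurgery" and Aim 3 says "Head injury that resulted in the loss of consciousness for more than 10 minutes". The documents do not show which rule is the looser, or that clinical judgement of severity is inadequate, so it forms no part of this point.

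**Conclusion.** The point holds as a minor safety-consistency matter. The implant item is the firm part: Aim 3 has a narrower written rule for the same devices, rTMS site, rTMS intensity and tDCS dose, with three times the active pulses and no stated safety reason. The migraine item is weaker, a difference in naming that other criteria may already cover.

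The narrower rule applies to up to 10 subjects. The number actually affected is unknown and may be zero. The documents give no prevalence of implants or migraine in this pool, so no count is attempted.

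A reader might infer that Aim 3 admits people with migraine or unsafe implants, or that the headache rates in the risk sections measure the harm. Neither is supported. The TASS items are unseen, and those rates describe side effects in general, not the effect of a missing exclusion. Nothing here suggests that anyone has been harmed, and the analysis is unaffected.

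The conclusion assumes that the two lists are meant to guard against the same device risks. If the sponsor has a safety reason for the difference, stating it would settle the matter.

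**What to change.** Replace Aim 3 exclusion item 4 with the Aims 1 & 2 wording, "metal implants in the head or neck, a pacemaker". For consistency, add "severe or recurrent migraine headaches" to the Aim 3 exclusions. Keep the MRI metal screen as a separate step for those who are scanned. Re-check enrolled Aim 3 subjects against the revised items before their next session.

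The cost is one protocol amendment and a revised screening checklist. The downside is the possible loss of a few candidates from a closed pool of former 109033 participants; the documents do not allow a count.

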Study Design, Population, Apparatus and Investigational Plan

Aims 1 & 2.

Design: This is prospective, experimental design includes a block randomized, blinded, sham controlled, mixed effects model with sequential assignment to two treatment arms (1 or 10 Hz rTMS) and random assignment to three experimental conditions within each arm (Table 1).

Randomization: Subjects will be assigned sequentially to one of two parallel groups (1 Hz or 10 Hz rTMS: Table 1.5). Next, they will complete three experimental test sessions (Table 1). The order of test sessions is randomized. A minimum two week washout period will follow each session to minimize session to session carry forward effects.¹⁵ Washout can exceed two weeks.

[figure not shown]

Figure 1.5. Subject flow.

Study visits: Study visits will be to the transcranial magnetic stimulation laboratory, room 654-2, located on the 6th floor of the Biomedical II research building on the UAMS

Study Title: Regulating homeostatic plasticity and the physiological response to rTMS
 PI: [name]
 Institution: University of Arkansas for Medical Sciences
 Support: Department of Neurobiology and Dev. Scs.

campus. In total, there will be 4 study visits - 1 consent/screening visit and 3 laboratory visits per subject. The 3 laboratory study visits will be separated in time by a minimum of two weeks. The time required to complete a study visit ranges from 1 hour, when TMS/EEG is not collected, to 3.5 hours, when TMS/EEG is collected. TMS/EEG is recorded immediately before and after tDCS preconditioning, immediately following rTMS and after a 20-30-minute delay to examine the acute and lasting effects.

Subject flow: Twenty healthy subjects who meet the entry criteria and pass safety screening for tDCS and TMS will be enrolled (Figure 1.5). Ten subjects will be tested in each aim, with two parallel groups of 5 subjects receiving either 1 or 10 Hz rTMS. Two randomization lists of 10, each balanced between tDCS over TC and tDCS over DLFC, were generated based

on uniformly distributed random number generation in SAS v9.4. The first 10 recruited subjects will receive 1Hz rTMS treatment while the second 10 will receive

Experimental conditions & TMS/EEG assessments.								
Condition†	TMS/EEG	tDCS	TMS/EEG	rTMS	TMS/EEG	30 min delay	TMS/EEG	
1		sham		sham				
2		sham		active				
3		active		active				
Time (mins)	0	20	40	60	80	100	130	

Table 1. † The order of conditions is randomized. A 2 week washout separates each condition.

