Up to ten subjects with tinnitus who participated in a previous rTMS study (i.e., 109033) and who agreed to be contacted for future studies will be invited to participate. The design of Aim 3 is an, open-label, feasibility study with pre and post assessments. All subject visits will be to the TMS laboratory and the Brain Imaging Research Center (BIRC) of the Psychiatric Research Institute. There will be a total of four study visits to the TMS laboratory, with one visit including a walk to the BIRC for the MRI scan, and three follow-up phone calls, emails or text messages used to obtain tinnitus ratings. The time required for each visit ranges from 1 hour when TMS/EEG is not measured to 3.5 hours when TMS/EEG is measured. During the first visit, subjects will complete the informed consent process and reestablish that they meet inclusion and do not meet the exclusion criteria. They will then complete a baseline TMS/EEG recording and make analogue ratings of tinnitus awareness, loudness and annoyance. An MRI image of the brain may be acquired as part of the first or second visit. During visits 2-4, subjects will be treated with tDCS over the DLFC (2 mA for 20 minutes) prior to receiving rTMS over the TC (1800 pulses delivered at 1 Hz and 110% of motor threshold). Following the treatment during visit four, subjects will have their second TMS/EEG recording. The study endpoints are the same as those in Aims 1 and 2 except that actual ratings of tinnitus are used in place of the procedure for measuring tinnitus like perception in healthy subjects.

Study Population

Aims 1 & 2

Study subjects will be recruited via advertisement. Twenty (20) healthy subjects between the ages of 19-65 years will be recruited. Screening measures include the Transcranial Magnetic Stimulation Adult Safety Screen (TASS).³⁷ A request for medical records either from UAMS or an external service provider may be necessary to ensure that subjects do not meet exclusion criteria.

Inclusion Criteria

- 1) complete the informed consent process
- 2) men and women, age: 19–65 years (a range reflective of our tinnitus samples, (e.g., CLARA IRB# 109639 *PET-CT to target and validate TMS as treatment for Tinnitus*)
- 3) negative pregnancy test (female subjects of childbearing age must take a pregnancy test).

Study Title: Regulating homeostatic plasticity and the physiological response to rTMS
PI: [name]
Institution: University of Arkansas for Medical Sciences

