Patients will be asked to have a structural MRI scan. For safety reasons and prior to the MRI scan, subjects may have a training session in the MRI simulator to help habituate and train them to the MRI environment. Per the MRI Policies and Procedures, the decision of who will be acclimated in the MRI Simulator will be made by the Research Coordinators and PI on a case-by-case basis. The PI for the study will have final say in this decision. Before the MRI scan, participants will be given an explanation of the study's procedures and screened with the MRI Safety Form for metal objects and claustrophobia. Participants will also be screened with the SAFESCAN® ferromagnetic detector according to MRI Policy and Procedures. The participant will then lie supine in the scanner. Participants will wear noise-cancelling headphones for communication and view visual stimuli through a mirror attached to the imaging head coil. Participants will undergo an anatomic scan.

The method for rTMS stimulation of the TC and for establishing the motor threshold is also identical to that described for Aims 1 and 2 except that 1800 pulses are delivered rather than 900 pulses and only active stimulation at 1 Hz will be used.

tDCS preconditioning of the DLFC will be delivered immediately prior to rTMS stimulation of the TC for three days within a one week period. rTMS will be targeted over the TC as described for Aims 1 and 2. The same safety measures will be performed before and after stimulation on each day of treatment. Additionally, analogue ratings (using a 0-100 scale) of tinnitus awareness, annoyance and loudness will be obtained at baseline and before and after each treatment session. The same ratings will also be obtained via phone, text or email on day 2, day 9 and day 16 following the last treatment. The necessary length of treatment and the timing and methods used to assess tinnitus were adopted from a previous study (109033) to ensure that the data

Study Title: Regulating homeostatic plasticity and the physiological response to rTMS
PI: [name]
Institution: University of Arkansas for Medical Sciences
Support: Department of Neurobiology and Dev. Scs.

are comparable between studies.

To assess changes in cortical excitability, EEG without and with TMS will be recorded during the baseline visit and following treatment on visit four. The primary outcome measure for TMS evoked EEG and the equipment used to assess TMS evoked EEG are described next.

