A weak electrical current is applied to the brain via the scalp during tDCS using two or more surface electrodes. Current evidence shows that tDCS applied to motor and non-motor areas according to the present tDCS safety guidelines^{15;38} produces only minor adverse effects in healthy humans and patients with varying neurological disorders. One published safety study of tDCS, using stimulation parameters similar to this study, evaluated 103 subjects³⁰, and found no adverse effects on cognitive and psychomotor measures, nor EEG changes during or after 20 min of treatment. In a double-blind, sham-controlled study⁶¹ it has been shown that comparing tDCS and sham stimulation of the motor cortex elicited minimal discomfort and difference in the duration of tingling sensations. Another study summarized adverse effects of 567 tDCS sessions over motor and non-motor cortical areas (occipital, temporal, parietal) in 102 subjects who participated in tDCS studies⁶².

Likely: During tDCS a mild tingling sensation was the most common reported adverse effect (70.6%). Moderate fatigue was felt by 35.3% of the subjects. A light itching sensation under the stimulation electrodes occurred in 30.4% of cases.

Less likely: After tDCS, headache (11.8%), nausea (2.9%) and insomnia (0.98%) were infrequently reported.

Rare: Reviews of tDCS safety have not identified specific risks associated with electrodes; however, a scalp burn could occur via a loose connection if the plug came in contact with the scalp. We protect against this risk by using electrode holders that are embedded in the EEG cap which also ensure a good connection to the stimulator. The connectors are housed away from the scalp making the possibility of a burn highly unlikely.

Risks associated with EEG

Likely: Subjects experience discomfort associated with mild scalp abrasion to reduce electrode impedance. Minor wounds can occur due to abrasion.

Less Likely: The EEG cap holds electrodes in place via a chinstrap. Subject could experience pain at recording sites due to this pressure.

Rare: Abrasion might be sufficient to cause bleeding or cuts.

Risks associated with MRI

Likely: Subjects will recognize they are in a confined space.

Study Title: Regulating homeostatic plasticity and the physiological response to rTMS
PI: [name]
Institution: University of Arkansas for Medical Sciences
Support: Department of Neurobiology and Dev. Scs.

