All adverse events occurring during the study, will be recorded on the Adverse Event Case Report Form. Special reporting procedures are required for certain adverse events.

Identification of Adverse Events

Anticipated adverse events that a subject may experience include the following:

- *Scalp tingling, itching or burning, and less so fatigue and nausea, have been associated with tDCS.*
- *Mild pain and headache related to scalp muscle twitching have been associated with TMS.*
- *Hearing loss, changes in cognition and mood, and seizure have rarely been reported with repetitive TMS and are even less likely with single pulse TMS. They are mentioned here to be comprehensive.*

Serious Adverse Events

Each adverse event will be assessed for its seriousness using the criteria outlined below. The term serious adverse event is not synonymous with a "severe" adverse event, which may be used to describe the intensity of an event experienced by the subject. An adverse event will be classified as serious if it meets any of the following criteria:

- Results in, or contributes to, a death

Study Title: Regulating homeostatic plasticity and the physiological response to rTMS
PI: [name]
Institution: University of Arkansas for Medical Sciences
Support: Department of Neurobiology and Dev. Scs.

- Life-threatening (i.e., the subject was, in the opinion of the investigator, at risk of death at the time of the event, but it does not include an event that, had it occurred in a more severe form, might have caused death)
- Results in permanent disability or incapacity (i.e., permanent impairment of a body function or permanent damage to a body structure)
- Requires in-subject hospitalization or prolongs hospitalization
- Necessitates medical or surgical intervention to preclude a permanent disability or incapacity
- Results in a congenital anomaly or birth defect

A serious adverse event will be reported to the IRB within 24 hours of first learning of the event.

Non-serious adverse events are all events that do not meet the criteria for a “serious” adverse event.

The investigator must promptly notify its reviewing IRB of such an event as soon as possible, but no later than ten (10) working days after first learning of the event.

Severity

Each adverse event will be assessed for its severity, or the intensity of an event experienced by the subject, using the following.

1. **Mild:** Discomfort noticed, but no disruption to daily activity.

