2. **Moderate:** Discomfort sufficient to reduce or affect normal daily activity.
3. **Severe:** Inability to work or perform normal daily activity.

Deaths

The investigator will notify the and IRB as soon as possible, preferably within 24 hours but in no event later than 48 hours, of learning of subject’s death.

Eliciting and Reporting Adverse Events

The investigator will assess subjects for the occurrence of adverse events at each study visit. All adverse events (serious and non-serious) reported by the subject must be recorded on the source documents and CRFs.

Independent data safety monitoring

All device studies (IDEs) operate under a mandatory, independent data and safety monitoring plan. The independent monitor for the study will be a monitoring specialist in the office of research and regulatory affairs which operates in conjunction with the Translational Research Institute (TRI).

Study Title: Regulating homeostatic plasticity and the physiological response to rTMS
PI: [name]
Institution: University of Arkansas for Medical Sciences
Support: Department of Neurobiology and Dev. Scs.

1. The sponsor will conduct independent data safety and monitoring before the first subject is entered, after the first subject is tested, and following the next 3–5 subjects entered.
2. The Data and Safety Monitoring Plan describes operating procedures that will be in place to monitor compliance, study data validity and integrity, participant safety, individuals and/or entities (e.g., IRB) that will be involved in monitoring these procedures, and the frequency/regularity of this monitoring.
3. UAMS IRB regulations will be strictly adhered to in the conduct of the proposed research. Specifically, prior to implementation of any protocol changes, amendments will be submitted to the IRB for approval.
4. In terms of participant safety, if an adverse event occurs during the course of a study, guidelines in the UAMS IRB Investigator's Handbook for adverse event and serious adverse event reporting will be followed. The PI will report all such activities to the IRB and the sponsor (as appropriate). Additionally, the PI will inform the sponsor of any actions taken by the IRB resulting from its continuing review of this study.

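### Adverse events are asked about only at study visits, and the last visit is always a stimulation session, so effects that begin after it are recorded only if the subject volunteers them

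*Combined protocol and SAP*

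**What the plan says.** The protocol's section Eliciting and Reporting Adverse Events ties active enquiry to visits: "The investigator will assess subjects for the occurrence of adverse events at each study visit". It then covers what subjects bring up themselves: "All adverse events (serious and non-serious) reported by the subject must be recorded on the source documents and CRFs". Adverse Events Reporting and Evaluation sets the wider intention: "All adverse events occurring during the study, will be recorded on the Adverse Event Case Report Form". No end of that period is stated, and neither is a safety contact after the last stimulation.

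For Aims 1 and 2, Study visits gives the schedule: "In total, there will be 4 study visits - 1 consent/screening visit and 3 laboratory visits per subject", and "The 3 laboratory study visits will be separated in time by a minimum of two weeks". Nothing is scheduled after the third laboratory visit.

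For Aim 3, the design section counts four laboratory visits, with treatment at visits 2 to 4. It lists separately "three follow-up phone calls, emails or text messages used to obtain tinnitus ratings". The Aim 3 procedures give their timing and content: "The same ratings will also be obtained via phone, text or email on day 2, day 9 and day 16 following the last treatment". The ratings are awareness, annoyance and loudness.

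Among the known effects of stimulation, Risks Associated with tDCS includes: "After tDCS, headache (11.8%), nausea (2.9%) and insomnia (0.98%) were infrequently reported".

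**The concern.** The protocol intends every AE during the study to be recorded, but the only scheduled enquiry happens in the laboratory. For every session except the last, the next visit gives a chance to ask what happened after the subject went home. For the last session there is no such chance. Insomnia is the clearest example, because it cannot be observed before the subject leaves; a headache that starts that evening is another.

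What is at stake is how complete the safety record is for this combination of stimulation methods. The section on what is unique about the proposal says that earlier preconditioning work targeted motor cortex, and the description of the test articles says that it used 1 mA. This study uses 2 mA over temporal and frontal targets, so its own safety data have value. In Aim 3 the final treatment is also the point of greatest cumulative exposure, and the contacts that could capture later effects are already in the schedule.

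**Working it through.** The plan states no figure to reproduce. The check sets the AE rule beside the visit schedules and counts the sessions left without a later enquiry.

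**1. Last visit against last stimulation**

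| | Aims 1 and 2 | Aim 3 |
|---|---|---|
| Visits | 1 screening + 3 laboratory | 4 laboratory |
| Stimulation at | each laboratory visit | visits 2, 3 and 4 |
| Last visit is a stimulation visit | yes | yes |
| Later scheduled contact | none | days 2, 9 and 16 |
| Stated content of later contact | not applicable | tinnitus ratings only |

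The Aim 3 contacts cannot be read as study visits, because the design section counts them separately from the four visits.

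**2. Sessions with no later scheduled AE question** (20 subjects in Aims 1 and 2, up to 10 in Aim 3; full enrolment and completion assumed)

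- Aims 1 and 2: 20 × 3 = 60 sessions, of which 20 × 1 = 20 are last.
- Aim 3: 10 × 3 = 30 treatments, of which 10 × 1 = 10 are last.

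**3. How many of these are active** (six condition orders assumed equally likely)

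- Active rTMS: 20 × 2 + 10 × 3 = 70 sessions. Expected last: 20 × 2/3 + 10 = 23.3, and 23.3 / 70 = 33%.
- Active tDCS: 20 × 1 + 10 × 3 = 50 sessions. Expected last: 20 × 1/3 + 10 = 16.7, and 16.7 / 50 = 33%.

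Each of the three conditions in Aims 1 and 2 falls last with probability 1/3, so each has an expected 20 / 3 = 6.7 last sessions.

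**4. Rough ceiling on events, under stated assumptions**

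The quoted tDCS percentages fit a denominator of 102 subjects (12/102 = 11.8%, 1/102 = 0.98%). The protocol describes a review of 102 subjects over 567 sessions.

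| Expected after a last active tDCS session | Percentage applied to every session | One report per affected subject over 567 sessions |
|---|---|---|
| Headache | 16.7 × 0.118 = 2.0 | 16.7 × 12/567 = 0.35 |
| Insomnia | 16.7 × 0.0098 = 0.16 | 16.7 × 1/567 = 0.03 |

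The headache figures still include headaches that start in the laboratory, which would be picked up there. The documents do not give the share that starts later. The figures also cover tDCS only; no rate is given for rTMS effects that begin after the subject leaves.

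**The case against.** The strongest reply is that the final session is well covered while the subject is present. It is itself a study visit, so the AE assessment applies. In Aims 1 and 2 the subject stays for TMS/EEG straight after rTMS and again after a further 20 to 30 minutes. The post-rTMS neuropsychological battery and the inspection for after-discharge also apply, and Aim 3 repeats its safety measures after stimulation on each treatment day. Volunteered AEs must be recorded. Worsening tinnitus in Aim 3 would appear in the day 2, 9 and 16 ratings. All of this stands. A reader might infer that nothing is asked after the last stimulation, or that delayed effects are missed altogether. The documents support neither: the gap opens when the subject leaves, and such effects are not actively elicited rather than lost.

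A reader might also infer that AE counts are biased between conditions, because a condition given last has no later enquiry. The documents do not support that. Order is randomized, so each condition has the same 1/3 chance of being last and any difference is chance imbalance. Analyses and Power calculations plans no AE comparison by condition.

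Nor should 11.8% be applied to all 30 subjects (30 × 0.118 = 3.5) to claim three or four unseen headaches. That counts headaches after any session, whereas only about a third of active sessions are last.

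It can also be said that several listed risks are described as short-lived: TMS head and neck pain is typically confined to stimulation, and possible cognitive effects last up to an hour. This narrows the point to effects such as later headache and insomnia. Finally, the protocol refers to standard operating procedures, an IRB handbook and a monitoring plan that may contain reporting instructions, and it allows staff to call subjects for follow-up. None of that, as described in the protocol, is a scheduled AE enquiry after the last visit.

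**Conclusion.** The point holds as an inexpensive improvement to safety data collection. As written, the plan schedules no AE question after the subject leaves the final stimulation visit in any aim. This affects 20 of 60 sessions in Aims 1 and 2 and up to 10 of 30 treatments in Aim 3, assuming full enrolment and completion. AEs that begin after those sessions enter the record only if volunteered. The consequence is incomplete ascertainment of delayed effects of the final session. It leaves the LMFP endpoint untouched and does not systematically favour one condition. The number of events affected cannot be derived from the documents. The range above, with its assumptions on tDCS rates, suggests that it is small.

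**What to change.** - **Aim 3:** add one open AE question to the contacts already scheduled on days 2, 9 and 16, with answers entered on the AE case report form.
- **Aims 1 and 2:** add one brief AE contact by phone, text or email at a fixed short interval after the last laboratory session. Day 2 would match the first Aim 3 contact.
- **Wording:** in Eliciting and Reporting Adverse Events, extend the rule to 'at each study visit and each follow-up contact'.

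Contacts after all 60 sessions in Aims 1 and 2 are not needed to close this gap, since the first two sessions are followed by another visit. They would be worth considering only if AEs were to be compared by condition, where equal collection windows would matter.

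The cost is a protocol amendment with IRB approval, about 20 short messages in Aims 1 and 2, one extra question at up to 10 × 3 = 30 existing contacts in Aim 3, and staff time to review and record replies. Sample size, stimulation and endpoints do not change.
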